The risk of serious side effects of respiratory depression with concomitant use with opioids is acknowledged (BC Children's Hospital Integrated Pain Service Gabapentin Information http://www.bcchildrens.ca/Pain-Services-Site/Docu-Sheet. Accessed at: ments/BCCH1455Gabapentin.pdf. Retrieved on October 4, 2020). A minority of patients might be on opioids. Dose adjustments will be added when gabapentin is used with a concomitant opioid or other CNS depressant medication: the family will be advised to return to the previous stable, safe dose in the protocol, and the subject will remain at that dose with no further escalation for the duration of the trial arm. This schedule will be duplicated on the parallel arm (active drug or placebo) to maintain masking. The participants are highly monitored, often with continuous oxygen saturation monitoring and/or "baby-cam" devices observing them during sleep. During the daytime they are with family, or professional caregivers (aides, nurses, etc.). These individuals will be advised to watch for respiratory depression and sedation that occur well before fatal apnea, and how to respond.

While there are no prohibitions on concomitant care, any care or medications unrelated to the trial will be noted in the CRFs for each participant.

Participants are sometimes obtaining respite care at facilities with nursing and physician care. Medical reconciliation is done at each admission. Parents will be provided with a letter to share with these programs outlining the study, the drug being tested, and a 24-hour pager to contact for further information or concerns

Active Participants < 15kg in mg per kg

Day	Morning mg/kg	Noon mg/kg	Evening mg/kg	Total mg/kg per day	% Change
1*	0	0	5	5	0
2	0	5	5	10	100%
3	5	5	5	15	50%
4	5	5	5	15	0%
5	5	5	10	20	33%
6	5	5	10	20	0%
7	5	5	10	20	0%
8	10	10	10	30	50%
9	10	10	10	30	0%
10	10	10	10	30	0%
11	13.3	13.3	13.3	40	33%
12	13.3	13.3	13.3	40	0%
13	13.3	13.3	13.3	40	0%
14	17	17	17	50	25%
15	17	17	17	50	0%
16	17	17	17	50	0%
17	20	20	20	60	20%
18	20	20	20	60	0%
19	20	20	20	60	0%
20	13.3	13.3	13.3	40	-33%
21	6.7	6.7	6.7	20	-50%
22	0	5	5	10	-50%
23	0	0	5	5	-50%
24	0	0	0	0	-100%
25	0	0	0	0	0%
Switch over*	-	-	-	-	-

^{*}Day one or 26 if switching over, not both.

Active Participants > = 15kg in mg per day

Day	Morning mg	Noon mg	Evening mg	Total mg/kg per day	Total mg/day	% Change
1*	0	0	75	5	75	0
2	0	75	75	10	150	100%
3	75	75	75	15	225	50%
4	75	75	75	15	225	0%
5	100	100	100	20	300	33%

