6	100	100	100	20	300	0%
7	100	100	100	20	300	0%
8	150	150	150	30	450	50%
9	150	150	150	30	450	0%
10	150	150	150	30	450	0%
11	200	200	200	40	600	33%
12	200	200	200	40	600	0%
13	200	200	200	40	600	0%
14	225	225	225	45	675	13%
15	225	225	225	45	675	0%
16	225	225	225	45	675	0%
17	225	225	225	45	675	0%
18	150	150	150	30	450	-33%
19	150	150	150	30	450	0%
20	100	100	100	20	300	-33%
21	100	100	100	20	300	0%
22	50	50	50	10	150	-50%
23	25	25	25	5	75	-50%
24	0	0	0	0	0	-100%
25	0	0	0	0	0	0%
Switch over*	_	-	-	-	_	-

^{*}Day one or 26 if switching over, not both.

Inactive

Day	Morning mg/kg	Noon mg/kg	Evening mg/kg	Total mg/kg per day	% Change
1*	0	0	0	0	0%
2	0	0	0	0	0%
3	0	0	0	0	0%
4	0	0	0	0	0%
5	0	0	0	0	0%
6	0	0	0	0	0%
7	0	0	0	0	0%
8	0	0	0	0	0%
9	0	0	0	0	0%
10	0	0	0	0	0%
11	0	0	0	0	0%
12	0	0	0	0	0%
13	0	0	0	0	0%
14	0	0	0	0	0%
15	0	0	0	0	0%
16	0	0	0	0	0%
17	0	0	0	0	0%
18	0	0	0	0	0%
19	0	0	0	0	0%
20	0	0	0	0	0%
21	0	0	0	0	0%
22	0	0	0	0	0%
23	0	0	0	0	0%
24	0	0	0	0	0%
25	0	0	0	0	0%
Switch over*	0	0	0	0	0%

^{*}Day one or 26 if switching over, not both.

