3.4. Outcomes

1. Primary Outcome: The mean pain and irritability score on the NCCPC-R through days 11-19 on active drug compared to placebo.

[figure not shown]
An 11-point decrement in the NCCPC-R score with no rebound x 3 days is considered clinically meaningful minimum change (improvement).

Secondary Outcomes:

- 2. For patients who benefited from gabapentin, identification of the lowest dose that was effective in reducing pain scores, as shown by a improvement the NCCPC-R score compared to baseline during day 11-19 on active drug.
- 3. For patients who benefited from gabapentin, identification of the maximal effect dosage as measured by the largest improvement in the NCPCC-R score compared to baseline during days 11-19 on active drug.
- 4. Identification of the latency time in days to the onset of maximum relief of pain and irritability as measured by the NCCPC-R score over days 0-19.
- 5. Adverse Events Collection demonstrates the AE on treatment arm do not exceed the frequency found in the Product Monograph for children receiving gabapentin.
- 6. Exploratory Outcome: PROMIS-57 scores reported by parent/caregiver are improved on the treatment arm compared to the placebo arm.

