3.10. Statistical Methods

All data will be entered into a REDCap database, either directly from participants using a web-based entry system, or for those using paper, transferred from data collection sheets by a research assistant. The study cohort will be described in tables with descriptive statistics (mean, median and standard deviation) where appropriate. The primary method of analyzing the data was by systematic visual graphing of the pain scale over the exposure/placebo conditions. This is the method recommended by the CONSORT collaboration, extension for N-of-1 studies (CENT).⁵⁸

Data analysis for the primary outcome will be conducted within each N-of-1 trial and will also be aggregated across trials using measurements taken on days 11-19.

For each individual, the pain and irritability score on the NCCPC-R will be calculated over days 11-19 for both the treatment and control periods. These means will then be compared statistically using a Bayesian model, reporting the posterior mean difference using a non-informative prior for the means and variance. The posterior probability that the mean of the treatment is greater than the mean of the control will also be reported. Because of the use of non-informative priors, this analysis is very similar to a t-test.

We will also aggregate the means across participants using Bayesian linear mixed models in order to compare the average effect of the treatment as well as obtain better estimates of each individual's effect through borrowing of strength from others' data.

Additional analyses

Secondary outcomes will be assessed as follows:

- For each patient who benefits from gabapentin, the lowest dose that was effective in reducing pain scores will be calculated as the lowest dose that gives at least an 11 point reduction with no rebound over 3 days in the NCCPC-R score compared to baseline during day 11-19 on active drug. The set of lowest doses will be summarized descriptively.
- For each patient who benefits from gabapentin, the maximal effect dose will be calculated as the dose that gives the largest improvement in the NCPCC-R score compared to baseline during days 11-19 on active drug. The set of lowest doses will be summarized descriptively.

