- The latency time in days to the onset of maximum relief of pain and irritability as measured by the NCCPC-R score will be the day that gives the largest improvement in the NCPCC-R score compared to baseline during days 0-19 on active drug. The set of latency times will be summarized descriptively.
- Adverse Events will be compared between treatment arms descriptively.
- PROMIS-57 scores reported by parent/caregiver will be computed for each patient on each arm by averaging the scores taken on days 12, 16 and 19 and comparing these mean scores. The differences in mean scores between the treatment and placebo arms will be summarized descriptively.

Analysis population and missing data

For the primary outcome, any missing days will be excluded from calculation of the mean.

For secondary outcomes, missing values will be disregarded in the sense that only observed values will be used to compute the lowest dose, maximal effect dose, latency time and PROMIS-57 mean scores.

Analyses will use the intent-to-treat principle meaning that observations in a period will be ascribed to the treatment to which that period was randomized.

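### The maximal effect dose is chosen from active-period change alone, so passing time, and at 15 kg or more the step-down days, can decide which dose is named

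*Protocol*

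**What the plan says.** Protocol section 3.4 lists as a secondary outcome, for patients who benefited, "identification of the maximal effect dosage as measured by the largest improvement in the NCPCC-R score compared to baseline during days 11-19 on active drug". Section 3.10 turns this into a calculation: "the maximal effect dose will be calculated as the dose that gives the largest improvement in the NCPCC-R score compared to baseline", over the same window. Neither place says whether improvement is taken day by day or averaged over the days at a dose, and neither brings in the placebo period. The bullet's closing sentence then summarizes the lowest doses, which is the quantity of the bullet before it.

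The neighbouring latency outcome is explicitly by day: it "will be the day that gives the largest improvement in the NCPCC-R score compared to baseline during days 0-19 on active drug".

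The dose tables in section 3.3 fix the calendar. Under 15 kg, days 11-13, 14-16 and 17-19 are at 40, 50 and 60 mg/kg/day, and the first reduction comes on day 20 ("20 13.3 13.3 13.3 40 -33"). At 15 kg or more, the 40 mg/kg/day level begins on day 11 ("11 200 200 200 40 600 33") and the 45 mg/kg/day level on day 14 ("14 225 225 225 45 675 13"). The first reduction comes on day 18 ("18 150 150 150 30 450 -33"), so days 18-19 are at 30 mg/kg/day.

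Section 3.3 also says that a child who benefits below the maximal dose stays at that dose until the scheduled wean. Table 4 schedules the NCCPC-R on every day from 11 to 19, for all subjects and in both periods.

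**The concern.** Within the active period, dose and elapsed time move together. A child who improves for any reason (natural course, regression to the mean, a growing expectation in the parent who scores) will look best at whichever dose comes last in the window. Change from a single baseline cannot separate this from a dose effect. The placebo period could, because it is scored on the same study days, but the rule does not use it.

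At 15 kg or more, the last dose in the window is not the highest but the first step of the wean. A child who keeps improving would have a step-down dose recorded as the maximal effect dose.

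Section 2.2 ties this outcome to the objective of identifying optimal dosing, and section 2.1 expects the results to help design a larger trial, including its dosing. A dose picked by calendar position would mislead that use.

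**Working it through.** **Inputs.** Dose by day and weight band come from the section 3.3 tables, and the window of days 11-19 from sections 3.4 and 3.10. Section 3.6 states that no prior data on day-to-day variability exist, so SD and trend are assumptions here. The protocol gives no figure of its own for this outcome, so there is none to reproduce. All scenarios follow the full schedule with no hold, use independent normal daily scores, and apply no restriction to children who benefit. Simulations used 200,000 children per scenario.

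**Step 1: no drug effect, no trend, best single day.** Each of nine days is equally likely to be best, so days per level set the answer.
- Under 15 kg: 3/9, 3/9, 3/9 = 33% each at 40, 50 and 60.
- 15 kg or more: 3/9 = 33% at 40, 4/9 = 44% at 45, 2/9 = 22% at the 30 step-down.

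**Step 2: no drug effect, improvement over time.** Take a trend of 0.25 SD per day. Under 15 kg, the three levels centre on days 12, 15 and 18, so adjacent levels differ by 3 × 0.25 = 0.75 SD from time alone. At 15 kg or more, the levels centre on days 12 (40), 15.5 (45) and 18.5 (30). The step-down level therefore gains 3.0 × 0.25 = 0.75 SD over the 45 level and 6.5 × 0.25 = 1.625 SD over the 40 level.

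| Trend (SD/day) | <15 kg, top dose named: best day / dose mean | ≥15 kg, taper dose named: best day / dose mean |
|---|---|---|
| 0.10 | 51% / 56% | 36% / 57% |
| 0.25 | 72% / 81% | 56% / 80% |
| 0.50 | 91% / 97% | 78% / 96% |

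The problem is present under either reading of the rule, and averaging without a placebo contrast makes it worse.

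**Step 3: is dropping the step-down days enough?** No. At 15 kg or more, with levels 40 (3 days) and 45 (4 days) averaged in the active period only, time separates them by 3.5 × 0.25 = 0.875 SD. The standard error of the difference is √(1/3 + 1/4) = 0.764 SD. The 45 level is then named with probability Φ(0.875/0.764) = Φ(1.146) = 87%, although the drug does nothing.

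**Step 4: subtract the placebo average on the same days.** A trend shared by both periods cancels. With no drug effect, selection returns to 33/33/33% under 15 kg and 50/50% at 15 kg or more, whatever the shared trend.

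**Step 5: a real dose effect.** Assume an effect linear in dose reaching 11 points at the maximum, with no trend. The best-day rule names the truly best dose in 59% (SD 4), 47% (SD 8) and 40% (SD 16) under 15 kg, and in 64%, 55% and 50% at 15 kg or more. The step-down dose is named in 6% to 17%. With a trend of 0.25 SD per day added at SD 8, the step-down dose is named in 40%.

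**Step 6: price of the fix.** A three-day level mean has standard error SD/√3 = 0.58 SD. After subtracting a three-day placebo mean it is SD × √(2/3) = 0.82 SD, larger by a factor of √2. With the dose effect of step 5 and no trend, the hit rate under 15 kg at SD 4 is about 57% to 58%, against 59% for the best-day rule.

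**The case against.** Several objections have force.

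- A reader might infer that the rule takes the single best-scoring day. The text does not say so. Only the latency outcome names a day, and how scores at one dose are combined is a detail that an analysis plan could settle. The point therefore does not rest on that reading.
- A reader might add that the best of nine scores lies about 1.5 SD below the child's mean by chance. That is true of the extreme score, but the outcome reported is a dose. The same baseline is subtracted on every day, so this inflation does not change which dose is named.
- A reader might conclude that noise and time decide the dose instead of the drug. That goes too far: at an assumed SD of 4, the rule finds the truly best dose in 59% to 64%, against 33% to 44% by chance.
- The hold rule and the restriction to children who benefit narrow the problem. A child held before day 11 has one dose in the window apart from any wean days, so there is little to choose between. The percentages above do not model this. Sections 3.4 and 3.10 do not, however, define benefit against placebo, so children who improve for other reasons can enter.
- The taper point does not apply under 15 kg, where the reduction starts after the window.
- The plan does look at dose against placebo elsewhere. Section 2.2 intends a comparison along the dose range, and section 3.10 makes graphs over both conditions the main method. A reader of the graphs will see the placebo course, but the calculated dose ignores it.
- The outcome is secondary and descriptive, in ten children. The fix also still names a dose for every child.

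These points limit the size of the problem. They do not remove the confounding of dose with time, or the step-down days in the window.

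**Conclusion.** The concern holds in this form: for children whose dose still changes within days 11-19, the maximal-effect-dose rule cannot tell a dose effect from improvement over time. At 15 kg or more, it can also name a step-down dose. With no drug effect and an assumed 0.25 SD improvement per day, it names the top dose in about 72% of children under 15 kg and the taper dose in about 56% at 15 kg or more (80% with dose means). At 0.10 SD per day the best-day figures are 51% and 36%. All of these assume the full schedule, independent days and no selection of children who benefit.

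This deserves correction because the outcome carries the optimal-dosing objective and the remedy uses data already collected. It does not touch the primary outcome.

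**What to change.** Reword the maximal-effect-dose bullet in section 3.10, and section 3.4 to match:

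1. For each child and dose level in the window, average the NCCPC-R scores at that level and subtract the average placebo-period score on the same study days. The maximal effect dose is the level with the largest reduction relative to placebo.
2. Leave step-down days out of this analysis, and reconcile the day 11-19 window with the dose table for 15 kg or more.
3. Report children held at one dose throughout the window separately, as offering no dose comparison.
4. Make the bullet's closing sentence summarize the set of maximal effect doses instead of the lowest doses.
5. Label the result as descriptive.

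The cost is wording only, with no new assessments. The statistical price is noisier level estimates (standard error up by about √2, with three or four scores per level), and at 15 kg or more only two levels remain to compare. The contrast removes a time trend only as far as both periods share it; improvement confined to one period would remain. The fix takes out shared-trend and taper bias but does not make any one child's dose selection reliable.

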2.2. Objectives

The primary objective of the trial is to evaluate the effectiveness of gabapentin to decrease pain and irritability in children with SNI, when the source of pain and irritability is attributed to neurological dysregulation (nociplastic pain), as measured by parent reported pain scores. This objective corresponds to the primary outcome listed in section 3.4.1.

We will compare the gabapentin versus placebo along an escalating dose range for both individual subjects and for the group. We will aggregate the results of the completed N-of-1 trials across all subjects to estimate the group level comparative effectiveness of gabapentin in reducing pain and irritability.

The secondary objectives are to:

- 1. Identify the optimal dosing of gabapentin in reducing pain and irritability (Corresponds to secondary outcomes 3.4.2 and 3.4.3).
- 2. Identify the latency time for gabapentin to show effectiveness (Corresponds to secondary outcome 3.4.4).
- 3. Evaluate the safety and tolerability of gabapentin (Corresponds to secondary outcome 3.4.5).
- 4. An Exploratory objective will be to evaluate whether parent/caregiver stress and function improve if gabapentin reduces children's pain and irritability. This objective corresponds to the Exploratory outcome listed in section 3.4.6.

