Summary: This study uses a rapid and safe dose escalation to the widely accepted therapeutic range where evaluation of response will be undertaken with frequent scoring. Different maximal doses are used for children < or ≥ 15 kg, based on pharmacokinetic data. Doses are titrated to clinical effect or maximum target dose, whichever is lower. Once in the therapeutic range, doses change after 3 days if there is not an adequate reduction in symptoms. For any subject that obtains clinical benefit below maximal dose, then they will be held at that dose for the remainder of that period until such time as the scheduled wean begins. At the end of each treatment period there is a wash-out.

Starting Dose: The starting dose of gabapentin will be 5 mg/kg administered as oral liquid or via gastric or jejunal routes. On Day 1 of the study, the gabapentin will be administered once at bed-time and then increased according to the schedule shown in Table 1.

Dose Escalation: The dose will be increased every 3^{rd} - 4^{th} day in a step wise fashion of 13% - 50%, starting with the evening dose in order to accommodate sedation. The maximum dose for subjects will be as follows: < 15 kg to 60 mg/kg day and \geq 15 kg to 45 mg/kg/day. Dose titration will be to a maximum target dose (based on weight as described, < 15 kg, > 15kg) or to clinical effect, whichever is lower. The dose escalation scheme is based upon expert consensus and personal communication with [name], [name], and upon review with the BC Children's Hospital research pharmacist. \cdot , 56.

Some children with PIUO and SNI have been given gabapentin empirically by their health care provider, often without any subsequent, detailed assessment of benefit. Many times, the medication is continued because of its low side-effect profile and overall safety compared with other analgesics. If a subject is currently on gabapentin at the time of enrolment, and the parent/caregiver wants an evaluation of its effectiveness, then the subject can be enrolled in this study with the following approach:

After appropriate enrolment and consent, the subject will be weaned off of gabapentin, in a stepwise manner with 25% reductions in dose every 3rd day. Once they are no longer on the active drug, they will be randomized to active drug or placebo like all other study participants.

Gabapentin Risks and Precautions

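### For children held at the dose where they first benefit, outcome 3 is capped by the hold rule and cannot identify a maximal effect dose

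*Protocol*

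**What the plan says.** Section 3.3 (Regimen, Administration and Duration) titrates to the weight-based maximum "or to clinical effect, whichever is lower". In the therapeutic range, "doses change after 3 days if there is not an adequate reduction in symptoms". The hold rule reads: "For any subject that obtains clinical benefit below maximal dose, then they will be held at that dose for the remainder of that period", and the hold lasts "until such time as the scheduled wean begins". The design summary in section 6.2 repeats that escalation stops at an effective dose.

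Section 3.4 lists secondary outcome 3, for patients who benefited, as "identification of the maximal effect dosage as measured by the largest improvement in the NCPCC-R score" relative to baseline during days 11-19 on active drug. Section 3.10 gives the computation: "the maximal effect dose will be calculated as the dose that gives the largest improvement in the NCPCC-R score compared to baseline". Outcome 2, in the same children and the same window, is "the lowest dose that gives at least an 11 point reduction with no rebound over 3 days in the NCCPC-R score compared to baseline".

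Section 2.2 assigns the optimal-dosing objective to outcomes 2 and 3. The missing-data paragraph of 3.10 adds that only observed scores enter these calculations. The last sentence of the maximal-effect bullet announces a summary of the lowest doses, as the bullet before it does.

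**The concern.** A dose of maximal effect can be located only if doses on both sides of it are tried, or if the range is exhausted. The hold rule withholds every further escalation step from a child once benefit appears. Outcome 3 is then computed in those same children and reported under a name that implies a comparison with higher doses.

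If a higher step would have helped more, the reported value understates the dose of maximal effect, and nothing in the report would show it. The optimal-dosing objective would then appear to have two sources of evidence when, for held children, it has little more than one. Section 2.1 expects the results to inform a larger randomized trial that also looks at dosing, so a truncated dose read as a maximum could carry over into that design.

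**Working it through.** **Step 1: doses inside days 11-19, by hold level.** Inputs are the two active dosing tables in section 3.3 (for children of 15 kg or more, the table's mg/kg column) and the hold rule. All doses are in mg/kg/day.

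| Weight group | Held at | Doses on days 11-19 | Possible values of outcome 3 |
|---|---|---|---|
| < 15 kg | 15, 20, 30 or 40 | held dose on all 9 days | held dose only |
| < 15 kg | 50 | 40 on 3 days, 50 on 6 | 50 or lower |
| < 15 kg | not held | 40, 50, 60 on 3 days each | any of the three |
| ≥ 15 kg | 15 or 20, wean capped at held dose | held dose on all 9 days | held dose only |
| ≥ 15 kg | 15 or 20, wean read literally | held dose on 7 days, 30 on days 18-19 | held dose or 30 |
| ≥ 15 kg | 30 | 30 on all 9 days | held dose only |
| ≥ 15 kg | 40 | 40 on 7 days, 30 on wean days 18-19 | 40 or lower |
| ≥ 15 kg | not held | 40 on 3 days, 45 on 4, 30 on wean days 18-19 | any of the three |

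The tabulated wean for the heavier group starts on day 18, inside the analysis window. The text does not say what happens on those days to a child held below 30.

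**Step 2: can outcome 3 differ from the held dose where two doses are present?** The protocol gives no SD, so daily SDs of 3, 5, 8 and 11 points were assumed, and the reported dose was that of the single best day.

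- < 15 kg held at 50, mean improvement 0 to 8 points at 40 and 11 to 15 at 50: differs in 0% to 24%.
- ≥ 15 kg held at 40, mean improvement 11 points at 40 and 0 to 11 on the wean days: differs in 0% to 22%. The upper end checks by hand: with equal improvement on all nine days, the best day is a wean day with probability 2/9 = 22%.

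In both cases the alternative is a lower dose.

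**Step 3: how far can the cap pull the reported dose down?** Assume a child < 15 kg, three daily scores per step at 40, 50 and 60, and a hold when the step mean improvement is at least 11 points. With true falls m1 and m2 at the first two steps and daily SD s, the chance of reaching 60 is

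P = Φ((11 − m1)/(s/√3)) × Φ((11 − m2)/(s/√3)).

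- Falls 12/16/20, s = 3: 0.282 × 0.0019 = 0.0005.
- Falls 12/16/20, s = 6: 0.386 × 0.0745 = 0.029.
- Falls 6/12/16, s = 3: 0.998 × 0.282 = 0.281.
- Falls 6/12/16, s = 6: 0.926 × 0.386 = 0.358.

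P is the ceiling on the share reported at 60. Simulation, with the single best day deciding the dose, gives:

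| True falls at 40/50/60 | SD | Reported at 60, with hold | Reported at 60, no hold |
|---|---|---|---|
| 12/16/20 | 3 | 0.06% | 89% |
| 12/16/20 | 6 | 2.8% | 69% |
| 6/12/16 | 3 | 28% | 90% |
| 6/12/16 | 6 | 32% | 72% |

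In both response patterns the true largest fall is at 60. If step means decide instead of the best day, the no-hold shares rise to about 95% (SD 3) and 77% to 79% (SD 6).

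**The case against.** The strongest reply is that 3.10 does give a rule that covers every benefiting child, held or not, and that a value exists whenever scores exist. That stands. A reader might infer that outcome 3 cannot be scored for held children; the documents do not support this. The observed-values rule does not remove the difficulty, though: it deals with missing scores, not with doses that were never given.

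A reader might also infer that outcome 3 always equals the held dose. It does not for children < 15 kg held at 50 or children ≥ 15 kg held at 40, where a lower dose also falls in the window. Children who benefit only at the maximum are not held at all. Nor is it certain that no dose above the held dose can be returned: the literal wean for a heavier child held at 15 or 20 puts 30 on days 18-19.

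The hold trigger is also open. Section 3.3 speaks of clinical benefit and adequate reduction, and ties neither to 11 points. If the trigger differs, a child may meet the 11-point criterion and still be escalated, and outcomes 2 and 3 then separate. If instead the trigger is the 11-point criterion without rebound over three days, Table 4 schedules NCCPC-R only on days 1, 5 and 8 before day 11. Holds below 40 could then not be established on that scale, and the single-dose case shrinks to children < 15 kg held at 40.

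Finally, outcome 3 is descriptive in ten children, titration to effect is a deliberate choice, and individual graphs will show the dose at each outcome point. This limits the consequence but does not correct the label.

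**Conclusion.** The point holds in limited form. The hold rule caps the doses that escalation can test, and section 3.10 reports the best of those as the maximal effect dose. For most hold levels in the tables this repeats the held dose. Otherwise it gives the held dose or a lower one, with the literal-wean reading as the only exception. For held children, outcomes 2 and 3 together cannot identify an optimal dose.

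The cap follows from the text alone. Its size does not: the shares of 0.1% to 3% and 28% to 32%, against 69% to 90% without a hold, rest on assumed falls, SDs of 3 and 6, and an assumed 11-point trigger in the lighter group. Section 3.6 confirms that no prior variability or effect size was available. For a child ≥ 15 kg held at 40, only the 45 step goes untested, a rise of 13% in the dosing table.

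**What to change.** Amend section 3.10 and leave dosing as it is.

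- For held children, report outcome 3 as the best dose among those tested, censored at the held dose, with the note that higher doses were not tested.
- Report an uncensored maximal effect dose, within the protocol's range, for benefiting children whose escalation reached the maximum target dose or who were escalated beyond their first effective dose. If a child in the second group was later held and responded best at that later step, the value is again censored there. Requiring a step above the first effective dose in every case would leave essentially no child with a value.
- State the number of children held at each step.
- Change the bullet's last sentence so that it summarizes maximal effect doses.
- Reconcile the hold rule, the wean on days 18-19 for children ≥ 15 kg and the days 11-19 window, so that it is clear which dose each score is ascribed to. How the dosing passages are reconciled is for the investigators.

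The cost is some rewording of the analysis section, and fewer of the ten children with an uncensored value for outcome 3.
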